7.6 Handling of Missing Data in the Analysis

The analyses for this study will focus on study completers to estimate the effect of the 2-session, patient centered intervention. The primary endpoint will be based on acceptability and feasibility aspects of the study. We will use the intention-to-treat principle for analyses with all participants. After we examine patterns of missingness, we will use maximum likelihood with multiple imputation to account for missing data.

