7.5 Analysis Plan

Aim 1: Feasibility and acceptability will be measured by rates of enrollment (>50%), participant retention (>70%), intervention attendance (>70% attending at least 1 of 2 sessions), and intervention satisfaction (>75% reporting average satisfaction greater than the CSQ's midpoint).

Aim 2: First, data will be analyzed with the intention-to-treat principle and assessed for statistical assumptions and patterns of missingness, implementing Multiple Imputation with maximum likelihood if appropriate. Sample size justification. We may over-accrue to ensure that a total of up to 45 BCS complete the study. This pilot study will provide a preliminary estimate of the rate of AET initiation within one month from baseline. With up to 30 participants, the width of the exact 95% confidence interval (CI) for the rate of AET initiation at one month will be at most 37.4% (i.e., +/- 18.7%). If at least 24% of participants initiate AET within one month, the study will rule out a post-intervention initiation rate of lower than 10% based on the lower limit of the exact 95% CI. We will conduct exploratory analyses to examine whether participants' baseline characteristics are associated with AET initiation at one month using Fisher's exact tests and unpaired t-tests. For secondary outcomes, we will conduct paired samples t-tests to assess intervention-related changes in satisfaction with communication with clinicians and treatment, Necessity-Concerns Framework, perceived support, self-efficacy for managing side effects, and QOL from baseline to one-month post-baseline. In addition, we will use linear mixed effects regression models to evaluate the change in secondary outcomes across all three assessment time points. We will interpret 95% Confidence Intervals and Cohen's d effect sizes ($D = [(Mean 1) - (Mean 2)] / \text{pooled Standard Deviation}$), with magnitudes of 0.3, 0.5, and 0.8 for small, medium, and large effects, respectively. We will conduct sensitivity analyses to examine whether changes in outcomes are differ among racial and ethnic groups.

Participants will be given the opportunity to receive a summary of study results at the completion of the study. If a request is made, the study staff will provide the participant with an abstract of the study at the end of data collection and analysis.

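### Section 7.6 names both undefined study completers and all participants as the effect population without ranking them, and the precision statements in Section 7.5 hold at 30 analysed answers but not at every smaller number

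*Combined protocol and SAP*

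**What the plan says.** Section 7.6 (Handling of Missing Data) opens with "The analyses for this study will focus on study completers to estimate the effect of the 2-session, patient centered intervention". After a sentence on the primary endpoint it continues "We will use the intention-to-treat principle for analyses with all participants", and ends by saying that "we will use maximum likelihood with multiple imputation to account for missing data".

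Section 7.5 (Analysis Plan) states for Aim 2 that "data will be analyzed with the intention-to-treat principle", with imputation made conditional: "implementing Multiple Imputation with maximum likelihood if appropriate". For the one-month AET initiation rate it says that, with as many as 30 participants, "the width of the exact 95% confidence interval (CI) for the rate of AET initiation at one month will be at most 37.4"%. It adds "If at least 24% of participants initiate AET within one month, the study will rule out a post-intervention initiation rate of lower than 10"%, judged by the lower exact 95% limit. For the questionnaires, "we will conduct paired samples t-tests to assess intervention-related changes" from baseline to one month, and a linear mixed model is also planned across all three assessments.

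AET initiation is a single self-reported item on whether the woman is currently taking the drug (Section 5.2). Women are registered once the baseline assessment is complete (Section 4.3). Enrolment is up to 35 (Section 7.2), and Section 7.4 makes no allowance for unevaluable participants.

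**The concern.** Sections 7.5 and 7.6 give two answers to the question of whose data estimate the effect. The emphasis on completers in 7.6 and the leading place of intention-to-treat in 7.5 point in opposite directions, so the wording does not settle the order. *Completer* could mean a woman who attended both sessions, attended one, answered at one month or finished at three months, and each gives a different denominator. The imputation sentences do not say how a missing AET answer is handled. A Clopper-Pearson interval needs one whole-number count and one denominator, which multiply imputed data do not supply directly. Nor does the plan say whether the paired t-tests use observed or imputed pairs.

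Two analysts could therefore report different initiation rates from the same data, and could choose after seeing them. The stakes are the preliminary initiation rate and the effect sizes that Section 7.2 intends for planning a full-scale trial. A completer rate would be too high if non-starters are harder to follow up. The stated precision also depends on how many women answer, and the words around the 37.4% figure present it as a ceiling for smaller numbers as well.

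**Working it through.** **Inputs.** From Section 7.5: 30 participants, exact 95% interval, 37.4% width, and the 24% and 10% figures. From Section 7.2: up to 35 enrolled. From Sections 2.0 and 7.5: a retention target above 70%. Assumed, because the documents give no dropout data: 25 of 35 answering at one month (71.4%), and the answering proportions in step 3.

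**1. Reproduce the plan's figures.** For x initiators of n, the exact limits are the 2.5% quantile of Beta(x, n−x+1) and the 97.5% quantile of Beta(x+1, n−x).
- The widest interval at n = 30 is at x = 15: 31.3% to 68.7%, width 37.4%. This matches.
- 7/30 = 23.3% has lower limit 9.9%; 8/30 = 26.7% has lower limit 12.3%. At n = 30, at least 24% means at least 8 women, so the statement holds.

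**2. Fewer than 30 answers.** The maximum width is 37.4% at n = 30, 40.9% at n = 25 and 44.5% at n = 21. So 37.4% is the smallest maximum for any n up to 30, not the largest.

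The 24% statement, tested at the first count reaching 24%:

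| n | count | rate | lower limit |
|---|---|---|---|
| 21 | 6 | 28.6% | 11.3% |
| 22 | 6 | 27.3% | 10.7% |
| 23 | 6 | 26.1% | 10.2% |
| 24 | 6 | 25.0% | **9.8%** |
| 25 | 6 | 24.0% | **9.4%** |
| 26 | 7 | 26.9% | 11.6% |
| 27 | 7 | 25.9% | 11.1% |
| 28 | 7 | 25.0% | 10.7% |
| 29 | 7 | 24.1% | 10.3% |
| 30 | 8 | 26.7% | 12.3% |

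Between 21 and 30 answers it fails at 24 and 25.

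**3. Completer rate if non-starters are lost more often (assumed).** With true rate p, and proportions a of starters and b of non-starters answering, the rate among those answering is pa / (pa + (1−p)b).
- p = 0.24, a = 0.85, b = 0.70: 0.204 / (0.204 + 0.532) = 0.204 / 0.736 = 27.7%, with 73.6% answering.
- p = 0.24, a = 0.90, b = 0.65: 0.216 / (0.216 + 0.494) = 0.216 / 0.710 = 30.4%, with 71.0% answering.

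Counting missing as not initiated gives pa = 20.4% in the first case. That is 3.6 points too low, where completers are 3.7 points too high. It is a bound, not a correction.

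**4. Does imputation repair it?** With 35 registered, 25 answering and 7 initiating, imputation without covariates gives 28.2%, against 28.0% (7/25) among those answering. Unless the covariates explain who drops out, the bias stays.

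**5. The two denominators, exact intervals.** With 7 initiating:
- 7/25 = 28.0%, CI 12.1% to 49.4%, excludes 10%.
- 7/35 = 20.0%, CI 8.4% to 36.9%, does not.

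With 8 initiating, 8/25 = 32.0% (lower limit 14.9%) and 8/35 = 22.9% (lower limit 10.4%) both exclude it.

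**The case against.** The strongest reply is that this is a pilot whose initiation rate is expressly preliminary, that intention-to-treat and multiple imputation are already stated, and that one sentence ranking the populations would close the gap. Much of that stands. The primary endpoint is feasibility and acceptability, and the 10% statement is not a go/no-go rule. What does not stand is that the general imputation text settles the matter: it gives neither a rule for a missing AET answer nor a way from imputed data to the promised exact interval.

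Several stronger readings are tempting.

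- *The choice between completers and intention-to-treat by itself decides whether 10% is excluded.* With 6 of 25 initiating, the exact interval is 9.4% to 45.1%, while an imputed rate with a pooled logit interval gives 11.2% to 44.2%. But a logit interval on the same 25 women is also 11.2% to 44.2%. The difference is the interval method, and no logit interval appears in the plan. It is not evidence of a population effect. Nor should such an interval replace the exact one: at n = 25 and a true rate of 10%, the chance that the lower limit exceeds 10% is 3.3% for the logit interval and 0.9% for the exact one.
- *The plan's arithmetic is wrong.* It is not; both figures reproduce at n = 30. The failures at 24 and 25 answers come from the discreteness of the binomial and have nothing to do with how completers are defined.
- *Dropout will bias the rate upwards.* The documents do not show this. The direction is an assumption, and the retention target is not tied to the one-month AET item.
- *The 7/35 result is one of the plan's options.* It is not; the plan nowhere counts missing as not initiated.

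**Conclusion.** The concern holds as a bounded one. The current text names two populations for effect estimation, ranks neither and leaves completers undefined. It promises an exact interval that does not follow directly from the planned imputation. Under the assumed dropout patterns a true 24% would be reported among completers as 27.7% or 30.4%, with the proportion answering still above 70%. The size rests wholly on those assumed proportions.

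The precision finding needs no dropout assumption: 37.4% is right for 30 analysed answers and too narrow as a maximum for any smaller number, and the 24% statement is untrue at 24 and 25 answers. Only Aim 2 is affected. This should be fixed because the change is cheap and the initiation rate is meant to inform a later trial; it does not threaten the feasibility conclusions.

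**What to change.** Wording in Sections 7.5 and 7.6 only.

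1. In 7.6, delete the sentence focusing on completers and make all registered participants the population for Aim 2.
2. For one-month AET initiation, keep the exact 95% interval. Report the rate among women who answered the one-month AET item, and let that define completers. Beside it, report the rate over all registered women with missing counted as not initiated, labelled as a conservative bound and not a correction. Claim without qualification that 10% is excluded only if both intervals exclude it. Any imputed rate is supportive, with its pooling rule stated.
3. Take questionnaire change from the linear mixed model already planned, using all available data, with paired t-tests on observed pairs as supportive.
4. In 7.5, state that 37.4% applies to 30 women with a one-month answer, give the width for the number expected to answer, and note that the 24% statement fails at 24 and 25 answers.

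No visit, procedure or sample size changes. The cost is that the stated precision and the conservative bound look less favourable: in the example with 35 registered and 25 answering, 8 initiators rather than 7 would be needed for an unqualified claim.

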9.1 Suggested Clinician Email Template: Request to Approach

Addressing Non-Initiation of Recommended Adjuvant Endocrine Therapy for Patients with a Culturally Informed Intervention
PI: [name].

Dear [Dr./NP/PA PROVIDER NAME],

I am a research coordinator working with [name] on a study to promote the initiation of endocrine therapy with a virtual, 2-session, culturally informed intervention for breast cancer survivors. Participants must be fluent in English or Spanish.

Your patient(s) may be eligible for the study:

Name	MRN	DOB

I would like to approach her regarding the study. Please let me know at your earliest convenience if I should refrain from approaching this patient for any reason. If I do not hear from you, I will follow-up in person to request permission.

Study participation does not preclude you and the rest of the patient’s care team from medically treating the patient’s symptoms per your clinical judgment.

Please feel free to let me know if you have any questions or concerns. Additionally, I have included a brief attachment with more study information.

Thank you,
[name of study staff]

[name of study staff]
Clinical Research Coordinator
Massachusetts General Hospital
[study staff email]
[study phone number]

9.2 Clinician Handout

Addressing Non-Initiation of Recommended Adjuvant Endocrine Therapy for Patients with a Culturally Informed Intervention

Study Rationale

- Up to 30% of BCS do not initiate AET as recommended.
- BCS of a racial or ethnic minority are disproportionately less likely to initiate AET.
- AET initiation is a modifiable health behavior with established predictors, with some being more salient for minority BCS.
- Interventions to improve initiation to AET are needed and should be culturally sensitive.
- Based on a qualitative study, we developed a culturally competent, two-session, nurse-led intervention to promote AET initiation in a diverse sample of early-stage, hormone receptor-positive BCS who have delayed initiation or have hesitations about initiating.

Study Specifics

- This is a single-arm pilot study in which up to 35 patients will be recruited to participate in a two-session intervention with purposeful recruitment of racial/ethnic minorities.
- We will aim to have one-third of the participants identifying as a racial or ethnic minority, in order to enroll a representative sample of experiences and concerns.
- The intervention consists of 2, one-hour sessions delivered over videoconferencing with a nurse practitioner. If necessary, these sessions can be delivered in person or via phone.
- All patients will be asked to complete assessments at baseline, 1-month, and 3-months after enrollment.

What Is Needed from You as the Clinician?

- Approve or deny study staff request to approach potentially eligible participants
- Refer patients you think may be eligible and a good fit for the study
- Provide care as usual

Patient Inclusion and Exclusion Criteria

- Female, age 21 or older, ability to read and respond in English or Spanish
- Diagnosis of early-stage (Stage I-IIIb), hormone-receptor positive breast cancer
- Recommended to start AET at least 3 weeks prior and not currently taking AET OR recommended to start AET in the future and reports hesitations to start AET as determined by a score of ≥ 4 (range =0-10) when asked "How hesitant are you about starting your recommended hormonal therapy? (0=Not at all hesitant and 10 = Extremely hesitant)"
- Eastern Cooperative Oncology Group (ECOG) performance status ≤ 2
- Does not have Stage 0 (DCIS) breast cancer
- May not have psychiatric or cognitive impairment
- May not have a psychiatric hospitalization within the past year
- Is not currently undergoing primary treatment for other cancer (i.e., advanced stage cancer)
- Is not participating in a clinical trial involving AET

Study Contact Information:

- Please send potentially eligible patients to the study coordinator [name and email] or to the study PI, [name], at [contact].

9.3 Rally Recruitment Portal Advertisement

Headline: Addressing Non-Initiation of Recommended Hormonal Therapy for Patients with a Culturally Informed Intervention

Summary: If you were diagnosed with breast cancer and have not yet begun taking a hormonal therapy, you may be eligible to participate in this research study. Participants will complete a brief, 2-session, culturally informed intervention.

Project Title: Addressing Non-Initiation of Recommended Hormonal Therapy for Patients with a Culturally Informed Intervention

Categories: Breast Cancer, Cancer, Medicines

Project Image:

Funding Source: Electronic Space Systems Corporation

Institutions conducting research: Massachusetts General Hospital, Dana-Farber Cancer Institute

IRB Organization: DF/HCC Dana Farber Cancer Institute

Recruitment start date: TBD

Recruitment end date: 5/1/2023

What are you studying?

We are studying a tailored, patient centered, culturally informed intervention for women who have not yet started taking hormonal therapy for breast cancer. This program will address challenges and barriers of beginning hormonal therapy.

Why is it important?

Patients diagnosed with breast cancer can experience a variety of challenges and barriers around beginning hormonal therapy. This program will allow women to explore and manage their specific concerns around starting these medications with a cancer center clinician.

9.5 Suggested Recruitment and Eligibility Phone Script

Hi, this is [Study Staff Name] calling from Massachusetts General Hospital/Dana-Farber Cancer Institute. Is this [Patient Name]?

A1. Self-referral call-back: Thank you for reaching out to our study team regarding the study. I would be happy to give you a brief overview of the study if you have a few minutes. Is now a good time?

IF YES: Continue to Section B.

IF NO: Is there a better time in the coming days I could give you a call back? [Continue to Section E.]

A2. Recruitment call: I am calling regarding a research study you might be eligible for that your oncologist, [provider name], thought you might be interested in. Is this a good time I could give you a brief overview of the study?

IF YES: Continue to Section B.

IF NO: Continue to Section E.

B. Study Description

This is a study about starting hormonal therapy, a type of medication that your oncologist recommended you take for breast cancer. This program consists of 2 sessions with a nurse over Zoom, to address any challenges or concerns you may be experiencing around beginning this medication. These visits would take place over a secure videoconferencing software Zoom. Does this sound like something you might be interested in?

IF YES: Continue to Section C.

IF NO: Continue to Section E.

C. Eligibility Pre-Screening

Thanks for your interest. To determine whether this study is a good fit for you, I am wondering, have you started taking the hormonal therapy prescribed to you by your oncologist?

IF YES: Continue to Section E.

IF NO: Continue in Section C.

On a scale of 0-10, with 0 indicating that you aren't at all hesitant and 10 indicating that you are extremely hesitant, how hesitant are you about starting your hormonal therapy?

IF ≥ 4 : Continue in Section D.

IF < 4 : Continue to Section E.

D. Consent Form Access and the Informed Consent Discussion

The next step is for us to go through the verbal consent process over the phone and I will send you a copy over email for your records.

IF YES: [Proceed to complete the verbal consent process]

IF NO: Okay, we can also complete the informed consent process through the mail. I will send you two copies of the consent form through the mail for you to sign both and send one back to me using a prepaid envelope I'll include. Additionally, I'll include the screening measures to verify your eligibility. [Collect address and continue to Section E]

E. Not Interested, Refusal, Paper-Consent Preference, Ineligible Outcome

Thank you so much for your time today. Please feel free reach out with any questions or concerns related to the study.

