2.0 Objectives

- Aim 1: To examine the feasibility and acceptability of the brief nurse-led intervention in BCS who have delayed initiation of AET or are hesitant to start (up to N=35) and refine the intervention using qualitative and quantitative feedback.

Hypothesis: The study will be feasible, defined by enrollment (rate>50%), retention (completion rate>70%) and attendance (≥70% of participants completing at least one session). The study will be acceptable as demonstrated by >75% of participants reporting average satisfaction scores greater than the mid-point of the Client Satisfaction Questionnaire (CSQ).

- Aim 2: To assess intervention-related changes in primary and secondary outcomes at one- and three-months post-baseline.

Hypothesis: Following the intervention, BCS will be more likely to have started their AET. We will explore changes in satisfaction with patient-physician communication, perceived social support, self-efficacy for symptom management, and quality of life.

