For patients meeting initial eligibility criteria and with clinician permission to approach, trained study staff will approach the patient at a clinic visit or by telephone to initiate the informed consent discussion and explain the study procedures. The study staff will first introduce the study to patients and ask if they have started taking their AET. If the patient indicates that they are not interested in the study, or are currently taking AET, study staff will collect the reason for refusal for the purposes of documentation and future study reporting. Depending on their reasons for refusal, study staff may request permission to re-approach some patients in the future, such as for later phases of this study.

For patients who engage via social media or are at other cancer institutions, they will self-report their age, diagnosis/staging, hormone receptor status, and ECOG score. We will aim to maximize recruitment of participants of a racial/ethnic minority via this method.

If the patient indicates that they are interested in the study and have not started taking their AET, the study staff

will screen the potentially eligible patient. Patients will be eligible if they have been recommended AET and have not started taking it within three weeks of the proposed start date, or if they are recommended to start AET in the future (e.g., post-radiation completion) and they have significant hesitations about starting AET. Hesitancy to start AET will be indicated by a score of ≥ 4 on the question, “how hesitant are you to start AET?” with 0 = not at all hesitant, and 10 = extremely hesitant. Once eligibility has been confirmed, the study staff will initiate the informed consent process verbally (if approached by telephone) or in-person (if approached in-clinic).

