7.0 Statistical Analyses

7.1 Primary and Secondary Endpoints

Our primary endpoint of this phase of feasibility and acceptability will be measured by rates of enrollment (>50%), participant retention (70%), intervention attendance (>70% attending at least 1 of 2 sessions), and intervention satisfaction (>75% reporting satisfaction greater than the CSQ's midpoint).

Our secondary aim is to assess intervention-related changes in primary and secondary outcomes at one- and three- months post-baseline. We will explore changes in satisfaction with patient-physician communication, perceived social support, self-efficacy for symptom management, and quality of life.

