9.6 Suggested Recruitment and Eligibility Phone Script - Spanish

Hola, mi nombre es [Study Staff Name] estoy llamando por parte de Massachusetts General Hospital/Dana-Farber Cancer Institute. Es usted [Patient Name]?

A1. Llamada de Autorreferencia: Muchas gracias por contactar a nuestro equipo sobre nuestro estudio. Si tiene algunos minutos, me encantaría darle un resumen corto sobre nuestro estudio. ¿Está disponible?

SI DICE “Sí”: Continúe a la Sección B.

SI DICE “No”: ¿Tendría algún momento en los próximos días en el pueda contactarme otra vez con usted? [Continúe a la Sección E.]

A2. Llamada de Reclutamiento: Estoy llamando sobre un estudio en el puede ser elegible para participar, y que su oncólogo, [provider name], pensó que a lo mejor le pudiera interesar. Si tiene algunos minutos, me encantaría darle un resumen corto sobre nuestro estudio. ¿Está disponible?

SI DICE “Sí”: Continúe a la Sección B.

SI DICE “No”: Continúe a la Sección E.

B. Descripción del Estudio

Este estudio esta relacionado con el comienzo del tratamiento hormonal, un tipo medicación que su oncólogo le ha recomendado que tome para cáncer de mama. Este programa incluye 2 sesiones con una enfermera a través de Zoom, individuales y culturalmente informadas para enfrentar cualquier desafío o preocupaciones que pueda estar teniendo al comenzar a tomar este medicamento. Estas visitas se realizarían a través de un software de videoconferencia segua utilizando Zoom. ¿Le interesaría participar?

SI DICE “Sí”: Continúe a la Sección C.

SI DICE “No”: Continúe a la Sección E.

C. Preselección de Elegibilidad

Muchas gracias por su interés. ¿Para determinar si este estudio es una buena opción para usted, le quería preguntar si usted ha empezado a tomar el medicamento de tratamiento hormonal que le prescribió su oncólogo?

SI DICE “Sí”: Continúe a la Sección E.

SI DICE “No”: Continúe a la Sección C.

En una escala del cero al diez, cero indicando que no tiene duda en absoluto y diez indicando que está sumamente indecisa ¿Qué tan indecisa está usted de comenzar su tratamiento hormonal?

Si ≥ 4 : Continúe a la Sección D.

Si < 4 : Continúe a la Sección E.

D. Acceso al Formulario de Consentimiento y Discusión Sobre el Consentimiento Informado

El próximo paso es de que revisemos el formulario de consentimiento y le enviaré una copia por correo electrónico para sus registros.

SI DICE “Sí”: Continúe en la Sección D. [Proceed to complete the verbal consent process]

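### The enrollment rate among eligible women can only be bounded, because decliners are not fully screened and the >50% criterion has no stated denominator

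*Combined protocol and SAP*

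**What the plan says.** Section 2.0 sets the criterion: "The study will be feasible, defined by enrollment (rate>50%), retention (completion rate>70%) and attendance". Section 7.1 makes it part of the primary endpoint, and Section 7.5 repeats it. None of the three gives a numerator, a denominator, or a rule for women whose eligibility is not known.

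The English script (9.5) describes the study in Section B and asks "Does this sound like something you might be interested in". A no goes to the closing, which is headed "E. Not Interested, Refusal, Paper-Consent Preference, Ineligible Outcome". AET status and the 0-10 hesitancy rating come only in Section C, after a yes. The Spanish script (9.6) has the same order, with the interest question "Le interesaría participar" in Section B.

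Section 4.1 orders the contact differently: "The study staff will first introduce the study to patients and ask if they have started taking their AET". It has staff record reasons for refusal. Screening, which includes the hesitancy item, then follows on this condition: "If the patient indicates that they are interested in the study and have not started taking their AET".

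Table 1, criterion 4, has two routes joined by OR. One is a recommended start at least 3 weeks ago with AET not being taken, which needs no hesitancy score. The other is a future start with a hesitancy score of 4 or more. The scripts send every score below 4 to the closing, whichever route applies.

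**The concern.** The natural reading of this criterion is whether more than half of eligible women enroll. Answering it requires knowing which of the women who declined were eligible. Hesitancy is not among the chart items listed in Section 5.2, so a decliner with a future start date cannot be classed on criterion 4. If the scripts are followed literally, a phone decliner's current AET use is not recorded either. This cannot be recovered after the call.

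The two available denominators err in opposite directions. Confirmed-eligible women are only those who first expressed interest, so that rate is too high. Approached women include some who are ineligible, so that rate is too low. With no denominator fixed in advance, the choice could decide whether a primary criterion is met, and the pilot is meant to support an application for a full-scale efficacy trial.

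**Working it through.** The >50% threshold has no derivation in the plan, so there is no figure to reproduce. The check is a bounding argument.

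**Inputs.** From the plan: threshold >50%; enrollment up to 35, so take N = 35 enrolled. Assumed, because the plan gives no counts:
- E = women confirmed eligible (interested and screened)
- I = women interested but found ineligible
- D = women who decline before screening
- q = share of D who are in fact eligible, which is not recorded

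**Formulas.**
- Rate among eligible women = N / (E + qD).
- Upper bound (q = 0) = N / E, that is, enrolled/confirmed eligible.
- Lower bound (q = 1) = N / (E + D).
- Enrolled/approached = N / (E + I + D), a valid but looser lower bound because it also counts women known to be ineligible.

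**When the verdict is open.** With N = 35, a rate above 50% needs a denominator below 70. The upper bound passes when E < 70, and the lower bound fails when E + D ≥ 70. If both hold, the verdict depends on q and turns at q = (70 − E)/D.

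| E | I | D | Enrolled/approached | q = 1 | q = 0.5 | q = 0 | >50% among eligible women? |
|---|---|---|---|---|---|---|---|
| 37 | 3 | 60 | 35/100 = 35.0% | 35/97 = 36.1% | 35/67 = 52.2% | 35/37 = 94.6% | Open; turns at q = 33/60 = 0.55 |
| 37 | 3 | 32 | 35/72 = 48.6% | 35/69 = 50.7% | 35/53 = 66.0% | 35/37 = 94.6% | Met at every q |
| 40 | 10 | 40 | 35/90 = 38.9% | 35/80 = 43.8% | 35/60 = 58.3% | 35/40 = 87.5% | Open; turns at q = 30/40 = 0.75 |
| 40 | 10 | 10 | 35/60 = 58.3% | 35/50 = 70.0% | 35/45 = 77.8% | 35/40 = 87.5% | Met at every q |

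At E = 37, the 33rd decliner brings the lower bound to 35/70 = 50.0%, which no longer exceeds 50%. The second row also shows why the lower bound should add only women of unknown eligibility: enrolled/approached falls below 50% there although the rate among eligible women cannot.

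**Whose eligibility is missing.**
- *Chart-screened, at least 3 weeks past the recommended start:* demographic and clinical criteria and the start date are known before contact (Section 4.1). Only current AET use may be missing, and Section 4.1, unlike the scripts, asks for it at the introduction.
- *Future start:* the hesitancy score decides eligibility and is missing for every decliner under either text.
- *Social media or other institutions:* age, stage, receptor status and ECOG score are self-reported (Section 4.1), so more may be missing.

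**The case against.** A reader might infer that the enrollment rate is wrong whichever denominator is used. The documents do not support that. The monitoring table in Section 6.0 has the number approached reported weekly, so enrolled/approached is a well-defined rate and a valid lower bound. If it exceeds 50%, the criterion is met on either denominator.

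A reader might also infer that enrolled/confirmed eligible must be near 100%. It need not be. Section B asks only about possible interest. Consent follows, sometimes by mail, and registration waits for the baseline assessment (Section 4.3). Losses at these steps lower the rate.

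Nor is decliners' eligibility wholly unknown, since chart pre-screening settles much of it for EHR-identified women. It does not settle everything: Section 5.2 lists neither hesitancy nor current AET use among the chart items, and Section 1.2 notes that non-initiation may come to light only at a visit 3-4 months after prescribing.

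It is fair to add that the scripts are labelled as suggestions and cover phone contact only, that the closing is a courtesy and not a data field, and that reasons for refusal or disinterest are collected. But Section 4.1 sends staff to these scripts to assess eligibility for Rally contacts, and a reason for disinterest is not an eligibility status.

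Finally, the size depends on assumed counts. The plan gives no decline rate, and it offers no evidence on whether ineligible or highly hesitant eligible women are more likely to refuse. That stands.

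**Conclusion.** The point holds as a measurement gap in a primary criterion with two joint causes: the denominator is undefined, and decliners are not fully screened. The scripts and Section 4.1 also conflict on when AET status is asked and must be reconciled.

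The consequence is a bounded rate, which is not necessarily a misleading one. With 35 enrolled, the >50% verdict among eligible women is open only if confirmed eligible is below 70 and confirmed eligible plus decliners is 70 or more. At 37 confirmed eligible, that means 33 or more decliners; at 60 decliners the bounds are 95% and 36%. These counts are assumptions, and with few decliners the question does not arise. The gap falls mainly on future-start women and on self-referred or outside-institution women. The change is worth making because it is cheap and the missing information cannot be recovered later.

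**What to change.** 1. Align 9.5 and 9.6 with Section 4.1. Ask AET status, and the 0-10 hesitancy item where the start date is in the future, before the interest question or of decliners willing to answer. Apply the same order to in-clinic approaches.
2. Reconcile the scripts' routing of every score below 4 to the closing with the OR in Table 1, criterion 4, so that women eligible on the delayed-start route are not logged as ineligible. Moving the questions earlier without this step would carry the conflict into the new denominator.
3. Log three outcomes separately: ineligible; eligible, declined; eligibility unknown. Women who end the call before the study is described will stay in the third group.
4. In Sections 7.1 and 7.5, define the rate as women enrolled divided by approached women found eligible, and state which event counts as enrolled. Report beside it the lower bound that adds women of unknown eligibility to the denominator.

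The cost is a minor script and protocol amendment and about one more minute per call. Some women will not answer before hearing more about the program. The partial HIPAA waiver in Section 3.1 is framed around record review, so the IRB submission should mention the added questions to women who have not yet expressed interest. The reported rate may be less favourable than enrolled/confirmed eligible.
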